3.4.5.2. Blinding

The treatments (IPs and control) will not be blinded to investigative personnel involved in the preparation/application and removal of treatments.

Investigative personnel who are involved in the preparation/application and removal of the treatments will not perform the evaluation of skin responses. Investigative personnel who are involved in the preparation/application and removal of the treatments will be unblinded. The trained evaluator who will be evaluating skin responses will be blinded to IPs and control and the

treatment allocation; however, because of the demarcations/skin coloration remaining on the skin following patch removal, complete blinding of the evaluators cannot be completely assured.

Investigative personnel, including the Investigator and trained evaluator involved in the evaluation of responses, will remain blinded during the course of the study until Database Lock and finalization of the Statistical Analysis Plan (SAP).

In the event of an emergency, if possible, the Investigator or designee will contact the Sponsor with notification of the intent to unblind the treatment codes prior to the actual unblinding. If it is not possible to notify the Sponsor prior to the unblinding, the Investigator or designee will contact the Sponsor immediately following the unblinding procedure and follow with a written notification to document the exact manner in which the code was broken and the justification for the unblinding. The Investigator will communicate the treatment identification to only the investigative personnel who require the information to manage the emergency. Unblinding will happen on site at TKL.

3.4.6. Prior and Concomitant Therapy

All medications, including over the counter (OTC) drugs and vitamins, taken within 28 days prior to the start of the study will be recorded at Screening. Thereafter, a record of all medications taken during the course of the study will be made. Information regarding the total daily dose, route of administration, start and discontinuation dates, and indication are to be captured on the subject's CRF.

The following prohibitions will apply for the duration of the study:

- There will be no use of systemic/topical anti-inflammatory analgesics which in the opinion of the investigative personnel will interfere with the study results, including anti-inflammatory medications such as aspirin (81 mg aspirin will be allowed at the discretion of the Investigator), Aleve, Motrin, Advil, or Nuprin for 72 hours prior to and during the study (occasional use of acetaminophen will be permitted);
- Use of sunbeds or sunlamps or deliberate exposure of the test sites to natural sunlight or to other sources of ultraviolet (UV) light;
- Participation in any other clinical study;
- Soaking of test areas; and/or
- Application of any product to the test areas.

The use of or change in the dose of any and all concomitant medication, either prescription or OTC, during the study will be recorded. The reason for use or change of dose of a concomitant therapy may need to be reported as an AE. Therapies (medication and non-medication therapies) not restricted by the protocol may be used. Non-prohibited chronic therapies being used at Baseline may be continued.

All topical or systemic medication listed in the exclusion criteria are prohibited during this study.

Refer to the IB for information about possible drug-drug interactions.¹

3.4.7. Treatment Compliance

All patches will be applied and removed by investigative personnel. Whereas bathing will be allowed (low tub bath/frontal showers), the patched areas are not to be soaked and are to be kept as dry as possible, per the instructions to be given to each subject. Subjects will be instructed to contact the Investigator before starting any medication, including OTC remedies. In the case of an emergency treatment, the Investigator must be informed as soon as possible. A trained, experienced evaluator will assess study compliance.

Records of patch applications and visit schedule compliance will be recorded on the subjects' CRFs.

If individual patches become dislodged or are misplaced, such that continuous contact with the skin has been interrupted, then patching at that site must be discontinued for the remainder of the study and that patch site will be considered not complete. If all patches become dislodged, the subject will be discontinued from further participation in the study.

3.5. Visit Schedule and Assessments

3.5.1. Study Procedures and Visit Schedule

Screening

At Screening, the subjects will receive any necessary written and verbal information, and the informed consent of each subject will be obtained. Demographic data (including Fitzpatrick skin type) will be recorded, a medical history will be taken, and previous and concomitant medications will be reviewed. Eligibility will be determined by review of the inclusion/exclusion criteria.

- Any written and verbal information
- Informed consent
- Demographics
- Previous/concomitant medication
- Review of inclusion and exclusion criteria
- Medical history (including lifestyle and habits)
- Examination of application site area

Table 1: Fitzpatrick Skin Types

I	Always burns easily, never tans
II	Always burns easily, tans minimally
III	Burns moderately, tans gradually
IV	Burns minimally, always tans well
V	Rarely burns, tans very well
VI	Never burn, deeply pigmented ^{4,5}

Day 1

Prior to randomization, women of childbearing potential will be administered a UPT. If the subject fulfills all of the inclusion and none of the exclusion criteria, he/she will be allowed participation in the study. A Baseline evaluation of the patch sites will be performed prior to application of the patches to ensure that no conditions, markings, or coloration of the skin will interfere with interpretation of the study results. Subjects will receive a unique randomization number, which determines the application scheme of the study materials for that individual subject.

A set of 4 application sites will be prepared in accordance with the randomization scheme on either the left or right side of the infrascapular area of the subject's back. The choice of left or right side will be made by the investigative personnel based on a visual inspection of skin clarity and will be recorded on the CRF to ensure consistent placement of the patches at subsequent visits. The distance between the patches will be approximately 1 cm. The numbering of the test sites will remain the same throughout the study. A surgical marker will be used to draw lines to indicate the 4 site locations for compliance purposes. All patches will be affixed to the test sites on the intact skin of the infrascapular area of the subject's back by the investigative personnel.

CCP-020 (Diacerein 1%) topical ointment and vehicle will be applied in the amount of 0.2 mL to a 2 cm x 2 cm Webril® patch pad via Eppendorf® Combitips and then applied to the subject's skin surface as soon as possible following product application. The sterile 0.9% saline (negative control) and 0.2% SLS (positive control) will be applied to a 2 cm x 2 cm Webril® patch pad via pipette and then applied to the subject's skin surface. All 4 products will be evaluated under occlusive patch conditions by means of application to a 2 cm x 2 cm Webril® pad. The patches will be secured with hypoallergenic tape as needed.

Days 2-21

The patches will be removed 24 ± 4 hours after application. Excess study material will be removed with a tissue to avoid the transference of materials between sites by investigative personnel. Investigative personnel responsible for patch application/removal will wipe each site with distilled water. A trained and blinded evaluator will perform an assessment of all test sites for irritation symptoms immediately (within 30 minutes) following patch removal using the scoring system detailed in [Section 3.5.5](#). Scores will be entered into the data sheets by the evaluator. If the skin is not disrupted (skin irritation score ≤ 2), identical treatments and patches will be re-applied to the same test sites with investigational products and control solutions using the procedures above. Separate individuals will be responsible for evaluation of the test sites (blinded) and patch application/removal (unblinded). Individual patches may be discontinued if a reaction of a grade of 3 or greater (see [Section 3.5.5](#)) occurs at any point during the study. Further patch applications of that product on that individual subject will be terminated. A NP symbol and a score of 3 will be assigned for all subsequent days.

The procedure for removal of study materials, evaluation of test sites, and application of fresh study materials will be repeated for 20 consecutive days, for a total of 21 applications per product per subject. A total of 21 post-baseline evaluation scores will be assigned to assess cumulative irritancy.

A new tube of CCP-020 [Diacerein 1%] topical ointment and vehicle will be opened every 14 days due to qualified suitability (see [Section 3.4.2](#)).

In addition, at each of the study visits, concomitant medications and AEs will be reviewed and recorded.

Day 22 (End of Study)

On Day 22 all patches and excess study material will be removed as described for Days 2-21, and the final evaluations of the test sites will be performed. A trained and blinded evaluator will perform an assessment of all test sites immediately following patch removal for irritation symptoms using the scoring system detailed in [Section 3.5.5](#). Scores will be entered into the data sheets by the evaluator.

An EOS examination will be conducted and consist of the following:

- Concomitant medication
- AEs
- UPT in females of childbearing potential

Concomitant medications and AEs will be reviewed and recorded during the whole study.

For a detailed listing of scheduled study time points refer to the Visit Schedule and Assessments ([Table 2](#)).

3.5.2. Visit Schedule

A summary of the visit schedule and assessments is presented in [Table 2](#).

Table 2: Visit Schedule and Assessments

	Screening Days -21 to -1	Treatment Phase Days 1-21	EOS Day 22 (or early termination)
Informed consent	X		
Demographics	X		
Inclusion/Exclusion	X	X ^a	
Medical history	X		
Randomization		X ^a	
Treatment applications and/or removals		X	X ^b
Evaluations		X	X
Concomitant Therapy/medications	X	X	X
Adverse events (AEs)		X	X
Urine pregnancy test (UPT)		X ^a	X

a: will be performed on Day 1 only (prior to first application).

b: treatment removal only

Note: The visit schedule may be revised if necessary.

3.5.3. Background Information

Date of birth, gender, race, Fitzpatrick skin type (see [Table 1](#)), and a significant medical history of each subject will be recorded at Screening.

3.5.4. Efficacy Assessments

No efficacy will be assessed in this study.

3.5.5. Safety Assessments

3.5.5.1. Local Tolerability Assessments

Assessment of the patch sites will be conducted by a trained evaluator once at Baseline (Day 1) and then 21 times post baseline during the study ([Table 3](#)). There will be a main evaluator for the study; a backup evaluator will also be assigned in the event that an emergency occurs and the main evaluator is unable to attend the study visit. The following symbols and their respective numerical equivalent Grades will be used to express the response observed at the time of examination ([Table 4](#)).

Table 3: Response Symbols and Numerical Equivalents

Grade	Score*	Definition
0	0	No evidence of irritation
1	1	Minimal erythema; barely perceptible
2	2	Definite erythema, readily visible; or minimal edema; or minimal papular response
3	3	Erythema and papules
4	3	Definite edema
5	3	Erythema, edema, and papules
6	3	Vesicular eruption
7	3	Strong reaction spreading beyond test site

*Scores are utilized only during the statistical analysis process of the study. Grades will be conducted throughout the study by the trained evaluator.

Table 4: Effects on Superficial Layers of Skin

Grade	Score*	Response
A	0	Slight glazed appearance
C	1	Marked glazing
E	2	Glazing with peeling and cracking
F	3	Glazing with fissures
G	3	Film of dried serous exudate covering all or portion of the patch site
H	3	Small petechial erosions and/or scabs

*Scores are utilized only during the statistical analysis process of the study. Grades will be conducted throughout the study by the trained evaluator.

Other notations (see [Table 5](#)) may be made in place of a score to designate particular circumstances preventing the assignment of a score or in addition to a score to identify damage to the epidermis and/or spreading of a reaction beyond the patch site.

The actual patch test grades are a combination of a numerical ([Table 3](#)) and letter ([Table 4](#)) grades consistent with the definitions given in the grading scales. However, in order to determine discontinuation of a patch site (grade > 3) and to perform statistical analyses, grades containing letter grades have to be converted to numerical equivalents. These are converted as follows: A=0, C=1, E=2 and F, G, and H=3. These equivalents are considered additive to any numerical score (e.g., 2C=2+1=3), in this case the patch site would be discontinued.

Table 5: Other Notations

Notation	Definition
X	Subject absent
B	Burning or stinging sensation
PD	Patch dislodged
NA	Patch not applied
NP	No patch due to limiting irritation
I	Itching
D	Damage of the epidermis: oozing, crusting, and/or superficial erosions
p	Papular response
pv	Papulovesicular response
S	Spreading of reaction beyond patch site (i.e., reaction where study material did not come in contact with skin)
T	Tape related reaction

Details regarding the statistical analysis of the cumulative irritation scores are provided in [Section 4.0](#).

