3.3.3. Interruption or Discontinuation of Treatment

In accordance with legal requirements and ICH-GCP guidelines, every subject or his/her legal representative has the right to refuse further participation in the study at any time and without providing reasons (see also [Section 5.3](#)). A subject's participation is to be terminated immediately upon his/her request. The Investigator should seek to obtain the reason and record this on the case report form (CRF).

If at the time of refusal a study product has already been administered, the subject should be advised on follow-up safety investigations. If a subject withdraws from the study, all efforts will be made to complete a final evaluation if possible. Subjects discontinued for having experienced an AE will be followed until the AE is resolved, a reasonable explanation is provided for the event, or the subject is referred to his/her own primary medical doctor (PMD). The specific AE in question will be recorded on the appropriate CRF.

If a subject develops a serious adverse event (SAE), his/her termination from the study will be considered by the Investigator. Similarly, if the subject develops conditions over the course of the study which would have excluded his/her entry in the study according to the safety-related medical exclusion criteria, he/she must be withdrawn immediately.

The subject may be withdrawn from the study at any time at the discretion of the Investigator for medical reasons and/or due to non-adherence to the treatment scheme and other duties stipulated in the study protocol. The reasons are to be documented on the CRF.

Individual patches may be discontinued if a reaction of a grade of 3 or greater (see [Section 3.5.5](#) for examples of values using additive grades from [Tables 3](#) and [Table 4](#)) occurs at any point during the study. Further patch applications of that product on that individual subject will be terminated. A “not patched” (NP) symbol and a score of 3 will be assigned for all subsequent days.

If a reaction is observed in any induction evaluation, a change in site location for the remaining applications in the Induction Phase will take place for that particular patch. See [Section 3.5.5](#) for interpretations of scores.

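### Section 3.5.5.1 prints the patch-stopping threshold as strictly above 3, against its own worked example and the 3-or-above rule in Sections 3.3.3, 3.5.1 and 4.6.1

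*Combined protocol and SAP*

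**What the plan says.** The rule for stopping a patch site appears in three places, and the analysis rule in Section 4.6.1 uses the same kind of boundary.

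- **Section 3.5.5.1** adds the letter equivalents (A=0, C=1, E=2, F, G and H=3) to the numeral "in order to determine discontinuation of a patch site (grade > 3) and to perform statistical analyses". Its example, 2C = 2+1 = 3, ends with the statement that "in this case the patch site would be discontinued".
- **Section 3.3.3**: "Individual patches may be discontinued if a reaction of a grade of 3 or greater" occurs. The next sentence reads: "Further patch applications of that product on that individual subject will be terminated". Section 3.5.1 repeats both sentences for Days 2-21.
- **Section 3.5.1** also gives the condition for carrying on: "If the skin is not disrupted (skin irritation score ≤ 2), identical treatments and patches will be re-applied to the same test sites". For a stopped site it adds: "A NP symbol and a score of 3 will be assigned for all subsequent days". Table 5 defines NP as "No patch due to limiting irritation".
- **Section 4.6.1**, last paragraph, sets a site's score at 3 for the rest of the study once its combined score has reached 3 or more.

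**The concern.** At each daily reading this rule decides whether a site stays under occlusion, for four sites per subject. Sections 3.3.3 and 3.5.1 both send the reader to Section 3.5.5 for the grading, so the odd threshold sits where staff are told to look.

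The stopping record also matters for safety. Under Sections 3.6.1, 3.6.2.1 and 3.6.6, a response that Tables 3 and 4 can describe is not an adverse event. Irritation strong enough to stop a patch is therefore documented mainly through grades and the NP code. If two staff members apply different thresholds to the same reaction, continued exposure and NP coding can differ.

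**Working it through.** **1. The plan's own example.** 2C = 2 + 1 = 3, so the sum reproduces. The stated consequence, stopping, does not follow from a threshold strictly above 3, because 3 > 3 is false. It does follow from 3 or above.

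**2. The statements side by side, at a combined value of exactly 3.**

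| Place | Boundary | Consequence at exactly 3 |
|---|---|---|
| 3.5.5.1, parenthesis | above 3 | threshold not met |
| 3.5.5.1, example 2C | total of 3 | stopped |
| 3.3.3 and 3.5.1 | 3 or above | threshold met |
| 3.5.1, re-application | 2 or less | condition not met |
| 4.6.1, last paragraph | 3 or above | score held at 3 |

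The parenthesis is the only outlier.

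**3. How many labels are affected.** Inputs: numerals 0 to 7 from Table 3 (8 values), and no letter or one of A, C, E, F, G, H from Table 4 (7 options). Labels: 8 × 7 = 56. Combined value = numeral + letter equivalent.

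- Total of 2 or less: 0, 0A, 0C, 0E, 1, 1A, 1C, 2, 2A = 9.
- Total exactly 3: 0F, 0G, 0H, 1E, 2C, 3, 3A = 7.
- Total above 3: 56 − 9 − 7 = 40.

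A threshold of 3 or above covers 7 + 40 = 47 labels and a threshold above 3 covers 40. They differ on 7 (7/56 = 12.5%).

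This reads the numeral as the Table 3 grade. The footnotes to Tables 3 and 4 support that, since they reserve scores for the statistical analysis. The conversion sentence does, however, speak of adding to a numerical score. With the numeral read as the Table 3 score, capped at 3, eight more labels (4, 4A, 5, 5A, 6, 6A, 7, 7A) also total exactly 3. The difference is then 7 + 8 = 15 labels (47 − 32), and no Table 3 response without a letter could ever exceed 3.

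**4. Effect on the primary variable.** Assume, for illustration, a site that scores 2 at every reading except a 3 at reading 10 of 21. Under the last paragraph of Section 4.6.1, nine readings count 2 and twelve count 3. The total is 9×2 + 12×3 = 54 and the mean is 54/21 = 2.57, whether or not the patch was stopped. Without that paragraph, a site left on and scored as observed would total 20×2 + 3 = 43, with a mean of 43/21 = 2.05. As the plan is written, the paragraph removes that difference.

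**The case against.** **The character may be an extraction fault.** The text examined was read from a PDF, and an at-or-above sign could have lost its bar. Other symbols survived in Section 3.5.1 ("The patches will be removed 24 ± 4 hours after application", and the at-or-below sign in the re-application condition). No at-or-above sign appears anywhere in the text, however, so its survival cannot be tested. This objection stands, and it is why the source check comes first.

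**The remaining text makes the intended boundary easy to infer.** The outlier is one parenthesis in a sentence about converting letters. The example beside it and the operating sections agree with each other. This also stands, and it limits the severity. It does not remove the conflict, because a decision threshold should not need inference.

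**Stronger readings that a reader might infer:**

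- *That seven labels have no instruction at all.* This follows only if the re-application limit of Section 3.5.1 is paired with the parenthesis in Section 3.5.5.1 while the 3-or-above rule in that same part of Section 3.5.1 is set aside. Staff who follow Section 3.5.1 have a rule for every label.
- *That* may *followed by* will *is a second contradiction.* The sentences read naturally in sequence: a patch may be stopped, and if it is, these consequences follow. The re-application limit and the 2C example point towards stopping. What is left is a drafting point.
- *That a site left on has no defined score.* Section 4.6.1 holds it at 3. Only its patching and NP coding are left unaddressed.

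**Conclusion.** The inconsistency is real as printed, and minor. The printed thresholds disagree only at a combined value of exactly 3: 7 of 56 labels on the grade reading, 15 of 56 on the score reading. These count possible labels and say nothing about how often such reactions will occur.

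What can differ is whether a site stays patched, its exposure, and use of the NP code. The number of stopped patches is not an irritancy output named in Section 4.6.1; at most it enters the descriptive compliance summary of Section 4.3.2.

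A reader might infer bias in the primary comparison. The documents do not support that: the effect on the mean and total cumulative scores is zero, provided the last paragraph of Section 4.6.1 is applied. The conclusion also assumes that the character in the source PDF is as it appears here.

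**What to change.** First check the character in the source PDF. If it is as printed, the sponsor should reconcile Sections 3.3.3, 3.5.1 and 3.5.5.1 so that one discontinuation threshold is stated everywhere. The *may be discontinued* and *will be terminated* wording in Sections 3.3.3 and 3.5.1 should be made consistent in the same edit. Which threshold or clinical rule applies is for the sponsor and investigator to decide; this review does not say.

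The cost is wording in three sections. Design, sample size, visit schedule and primary analysis do not change.

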3.6. Adverse Events

3.6.1. Method of Determining Adverse Events

Safety assessments will include recording AEs reported spontaneously by the subject or collected by the Investigator. AEs will be recorded at each visit throughout the study on the appropriate CRF. Every attempt should be made to describe the AE in terms of a diagnosis. If a clear diagnosis has been made, individual signs and symptoms will not be recorded unless they represent atypical or extreme manifestations of the diagnosis, in which case they should be reported as separate events.

Subjects should be asked whether, since the time of the last observation or visit, they had any of the following:

- Experience any changes in well-being;
- Used any new medications;
- Changed medication regimens (both prescription and OTC); and/or
- Were admitted to a hospital or had any accidents.

All questions should be of a general nature and should not suggest symptoms.

When an AE is suspected, all relevant evaluations will be carried out and appropriate treatment provided. Additional follow-up will be done as necessary ([Section 3.6.4](#)) and recorded in the subject's source documents, and the results will be provided to the Sponsor.

For AE definitions and reporting requirements refer to [Section 3.6.2](#) and [Section 3.6.3](#).

Note: Any observed response which can be denoted using the irritation criteria summarized in [Table 3](#) and [Table 4](#) will not be considered an AE. Likewise, any tape-related irritation will only be noted as an AE when all patches are discontinued due to tape reaction around all sites (see [Section 3.6.6](#)).

